5.4. Retests, unscheduled visits and early termination data

Scheduled visits, unscheduled visits, and early discontinuation visits will be used independently of the nominal visit.

5.5. Windowing conventions

As stated in section 5.1, the timing of visits for post-treatment follow-up visits will be determined from Study Day 0.

All visits originally planned in the protocol schedule of events have a visit window that was specified during data-review (see section 5.3). In the case of multiple records for a subject within a particular visit window, then the assessment that is closest to the target day will be used. In the event that both (or all) the records are equidistant from the target day then the latest of the equidistant records will be used.

5.6. Statistical testing

The default significance level will be (5%); 95% confidence intervals will be produced, and all tests will be two- sided, unless otherwise specified in the description of the analyses.

5.7. Common calculations

For quantitative measurements, change from baseline at visit X will be calculated as:

Test Value at Visit X – Baseline Value

5.8. Software version

The statistical analysis will be performed using the SAS[®] software (Version 9.4 or higher).

6. Statistical considerations

6.1. Multicenter studies

This study will be conducted by multiple investigators at multiple sites internationally. Sites will be pooled per region, i.e. by continent of Asia, Europe and the USA.

The effect of region in the association between treatment and primary endpoint will be examined (see section 13.1.5).

6.2. Missing data

For incomplete dates following convention will be used:

- Birthdate missing: if birthdate is missing but an age has been recorded in the CRF, the year of the birthdate will be imputed as the following:

Year of birth = year of screening – age at screening

The birthdate will then be imputed with this year and 1st of January as day and month of birth.

- Date of onset of vision loss for each eye:
 - For missing day: '01' will be imputed (if month is not missing).
 - For missing start month: 'January' will be imputed (if start year is not missing).
 - For affected eyes (i.e. excluding non-affected eyes at baseline), a missing date of onset of vision loss for one eye, will be replaced by the date of onset of vision loss of the contralateral eye.
- For AEs and CMs incompletes dates, see Appendix 2
- For other incompletes dates, no imputation will be performed.

Missing efficacy data will only be imputed as described in sections 13.1.3 and 13.2.2.

6.3. Multiple comparisons/ multiplicity

All the type I error ($\alpha=0.05$) will be spent for the primary endpoint analysis. Other analyses, including those performed at 2 years, described in section 15, will be performed as either secondary, sensitivity, supportive, or exploratory analyses with no multiplicity adjustment.

6.4. Examination of subgroups

Subgroups analyses will be performed. The following subgroups will be assessed for the primary endpoints (BCVA):

- Eyes on-chart for LogMAR BCVA at baseline,
- Eyes off-chart for LogMAR BCVA at baseline
- Pediatric (<18 years-old)/Adult populations,

- Males/Females,
- Previous idebenone treatment yes/no.

6.5. Covariance of subgroups

For the MMRM model, LMM and GLMM, autoregressive (AR(1)) covariance structure will be used to model the within-patient error and the Kenward-Roger approximation will be used to estimate the degrees of freedom. If the model assuming AR(1) covariance structure fails to converge, the following covariance structures will be tested one after the other in the order listed until one converges (remaining covariance structures will not be tested): heterogeneous autoregressive order 1 (ARH(1)), compound symmetry, heterogeneous compound symmetry (CSH), Toeplitz (TOEP), and heterogeneous Toeplitz (TOEPH).

7. Output presentations

Appendix 1 shows conventions for presentation of data in outputs.

The templates provided with this SAP describe the presentations for this study and therefore the format and content of the summary tables, figures, and listings to be provided by eXYSTAT.

8. Disposition and withdrawals

The total number of subjects enrolled, the numbers and percentages of randomized subjects (ITT population) who were treated in the study, who completed the 1.5-year visit will be provided with the numbers and percentages of randomized subjects who withdrew prematurely, and a breakdown of the corresponding reasons for withdrawal will be presented by treatment group and overall.

The numbers and percentages of randomized subjects who enrolled in the Follow-Up Period 2, who completed the 3-year visit, the 4-year visit, and Post-Treatment Follow-Up Period 2 (5-year visit) will be provided by treatment group and overall, together with the numbers and percentages of randomized subjects who withdrew from the study prematurely, with a breakdown of the corresponding reasons for withdrawal.

The number and percentage of randomized (ITT population) subjects in the mITT, PP, and safety populations will also be provided by treatment group and overall, together with the numbers and percentages of randomized subjects excluded from the analysis populations, with a breakdown of the corresponding reasons for exclusion.

A listing of subjects not included in the scheduled time windows will be provided for each visit concerned.

All major protocol deviations will be identified prior to unmasking for analysis. A supportive analysis of the primary endpoint will be performed based on the per-protocol analysis population. Subjects with major protocol deviations that can potentially interfere with the interpretation of the treatment effect will not be included in the PP analysis population. A listing showing protocol deviations for each subject will be provided by treatment group.

9. Demographic and other baseline characteristics

Demographic data and other baseline characteristics of the ITT populations will be summarized by treatment group and overall using descriptive statistics.

No statistical tests will be performed to examine any of the demographic or other baseline characteristics for a statistically significant difference between the treatment groups.

The following baseline characteristics will be reported for this study:

- Relevant medical and surgical history
- Prior medications (see section 13 below)
- Duration of disease at baseline (corresponding to the duration of vision loss at baseline for first affected eye): overall and by age classes at consent <15, [15-18[, [18-60[, ≥60-year-old
- Duration of vision loss at baseline of best eye
- Duration of vision loss at baseline of worst eye
- Duration of vision loss of first eye
- Duration of vision loss of second eye
- Time interval between first and second eye vision loss
- Prior use of Idebenone
- Duration of use of Idebenone
- Dose of Idebenone
- Time between stop date of Idebenone and baseline
- Bilateral/Unilateral affected eye status at baseline:

The following demographic characteristics will be reported for this study:

- Age at consent (years)
- Number of patients with age at screening <15, [15-18[, [18-60[, ≥60-year-old
- Age at onset of the disease
- Number of patients with age at onset of the disease <15, [15-18[, [18-60[, ≥60-year-old
- Gender
- Tobacco use
- Alcohol consumption.

Variables derivations:

- Age at consent (years)

Age at Consent = the largest whole number < (Date of informed consent-Date of birth)/365.25.

- Age at onset of the disease (years)

Age at onset of the disease the largest whole number < (Earliest date of onset of vision loss -Date of birth)/365.25.

- Alcohol consumption

For former and current use:

No use

≤1 drinks per day or occasionally

]1-2] drinks per day

>2 drinks per day

- Bilateral/Unilateral affected eye status at baseline

Unilateral eye affected: if $\text{LogMAR} \leq 0$ for one of the two eyes on the day of injection

Bilateral eyes affected will be derived as: if $\text{LogMAR} > 0$ for both eyes on the day of injection

- Duration of disease at baseline (months)

Duration of disease at baseline = date of baseline – earliest date of onset of vision loss

- Duration of vision loss at baseline for one eye (months)

Duration of vision loss at baseline for one eye = date of baseline – date of onset of vision loss for the considered eye

Demographic and baseline characteristics will be summarized using descriptive statistics. Categorical variables (e.g. gender) will be summarized using frequencies (count and percentages) while quantitative variables (e.g. age, tobacco use) will be summarized using number of subjects with available data (n), mean, SD, median, first quartile (Q1), third quartile (Q3), minimum, and maximum.

These data will be listed by treatment group.

10.Surgical and medical history

Medical and surgical history conditions are defined as those conditions which stop prior to or at Screening and will be coded to the system organ class (SOC) and preferred term (PT) using Medical Dictionary for Regulatory Activities (MedDRA) version 21.1 or later.

Medical and surgical history data of the safety analysis set will be summarized by SOC and PT using counts and percentages based on the number of subjects in each treatment group and overall.

11.Medications

The World Health Organization (WHO) drug dictionary version 01SEP2017EB3 or later will be used for medications coding. The Anatomical Therapeutic Chemical (ATC) classifications ATC2 and ATC4 will be used.

Prior and concomitant medications are defined as follows:

- Prior medications are defined as prescription and non-prescription medications and preparations, including health and/or dietary supplements, prior to first IVT.
- Concomitant medications and therapies are defined as prescription and non-prescription medications and preparations, health and/or dietary supplements other than randomized study treatment that the subject receives during the course of the study (i.e. any time after first IVT). This includes any medication started prior to first IVT and continued after first IVT.

See Appendix 2 for handling of partial dates for medications, in the case where it is not possible to define a medication as prior or concomitant, the medication will be classified by the worst case, i.e. concomitant.

Concomitant treatments will be summarized by coded terms using number and percentage of Safety population subjects by treatment group reporting the medication at least once during the study.

Incidence of corticosteroid therapy will also be presented by route of administration (local corticosteroid alone / Systemic corticosteroid alone / Local and systemic corticosteroid) for the first 6 months of follow-up and for the follow-up between 6 months and 1 year and for each year of follow-up after the first year. A patient will be counted in the “local and systemic corticosteroid” class if he took, during the time windows of interest, at least one local corticosteroid and at least one systemic corticosteroid, whatever the concomitance of these two treatments.

Description of local corticosteroid therapy will be presented using descriptive statistics:

- Duration of treatment (days),
- Reason of use of local corticosteroid (Preventive of ocular inflammation / for AE)
- Indication of use (Ocular/non-ocular)

Description of systemic corticosteroid therapy will be presented using descriptive statistics:

- Duration of treatment (days),
- Daily dose, for systemic corticosteroid therapy (expressed in dexamethasone dose equivalent)

INP	Equivalent Daily Doses	Factor to apply to convert in dexamethasone dose equivalent
Dexamethasone	0.75 mg	1
Cortisone	25 mg	0.75/25
Hydrocortisone	20 mg	0.75/20
Prednisone/Prednisolone	5 mg	0.75/5
Methylprednisolone	4 mg	0.75/4
Triamcinolone	4 mg	0.75/4
Betamethasone	0.75 mg	1
Cortivazol	0.3 mg	0.75/0.3

- Reason of use of systemic corticosteroid (Preventive of ocular inflammation / for AE)

Description of idebenone will be presented using descriptive statistics:

- Duration of treatment (days),
- Daily dose

Description of intraocular pressure lowering agents will be presented using descriptive statistics:

- Duration of treatment (days),

- Reason of use of intraocular pressure lowering agents (Preventive of intraocular pressure increase / for AE)

Listings of patients on corticosteroid therapy, Idebenone and intraocular pressure lowering agent will be provided.

12.Study medication exposure

In this study, each eye will undergo administration of the allocated treatment (GS010 or Placebo) with a single intravitreal injection, performed as a separate procedure. Therefore, no summary table will be produced for the exposure data. eCRF data related to GS010 administration will be listed.

13.Efficacy outcomes

All primary efficacy analyses will be conducted using the ITT population and on the primary eye, which is the second-affected/not-yet-affected eye. Data will be summarized at each visit and presented in tables; change from baseline will be calculated and the associated two-sided 95% confidence interval presented.

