#### 13.9.1 Immune Modulating Regimen

All subjects will receive a peri-treatment systemic oral immune modulating regimen for the prevention or diminution of ocular inflammation related to IVT injection of GS010. The immune modulating regimen will consist of oral corticosteroid starting 2-days prior to the initial treatment administration to any eye of the subject and will be completed after a 28-day immune modulating regimen. The following regimen will be administered:

- Immune modulating agent: corticosteroid
- Route of administration: per os (p.o.; i.e. orally)
- Administration regimen:

- 40 milligrams (mg) daily for 1 week, starting two days prior to treatment administration to any eye of the subject, then
- 30 mg daily for 1 week, then
- 20 mg daily for 1 week, then
- 10 mg daily for one week → then stop

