14.1. Adverse events

An adverse event (AE) is defined as any untoward medical occurrence in a subject or clinical investigation subject administered a pharmaceutical product and which does not necessarily have a causal relationship with this

treatment. An AE can therefore be any unfavorable and unintended sign (including an abnormal laboratory finding), symptom, or disease temporally associated with the use of a medicinal (investigational) product, whether related to the medicinal (investigational) product, or not. Any event or laboratory abnormality that leads to a medical intervention, including withdrawal of IMP or significant additional concomitant therapy, will be considered an AE. Worsening of visual acuity determined by the Investigator to be due to progression of LHON will not be considered an AE.

AEs should be volunteered by the subject, be observed from examination of the subject at a clinic visit or be from observations of clinically significant laboratory values or other/special examination abnormal values. AEs will not be solicited by use of a specific list of anticipated events.

AEs will be coded to the SOC and PT using MedDRA central coding dictionary, Version 21.1 or higher.

Treatment-emergent adverse events (TEAEs) are defined as AEs that started on or after study treatment administration at Visit 3 or that represent an exacerbation of a condition that is present at baseline after treatment administration. See Appendix 2 for handling of partial dates for AEs. In the case where it is not possible to define an AE as treatment emergent or not, the AE will be classified by the worst case; i.e. treatment emergent.

Local (i.e. ocular) and systemic (i.e. non-ocular) AEs will be summarized separately. Ocular TEAEs will be summarized by treatment group for the first affected eye and second-affected/not-yet-affected eye separately. Systemic TEAE data will be summarized for the 2 treatment groups combined.

The following summaries will be produced for systemic AEs and ocular AEs separately using counts and percentages, i.e. number of subjects and percentage of subjects.

- Overall summary of AEs for the entire study, including the number of events reported
- TEAEs, including the number of events reported
- TEAEs by relationship to study treatment ('Unrelated', 'Unlikely', 'Related')
- TEAEs by relationship to study procedure ('Unrelated', 'Unlikely', 'Related')
- TEAEs by severity
- TEAEs leading to study discontinuation
- Serious TEAEs

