14.1.6. Treatment for AEs related to elevation of IOP

Treatment of AEs with elevation of IOP will be described with number of patients using IOP lowering treatment (None/IOP agent lowering local alone/IOP agent lowering systemic alone/ local and systemic in association) for the first 6 months of follow-up and for the follow-up between 6 months and 1 year and for each year of follow-up after the first year.

Duration of treatment will be described.

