14.1.7. Treatment for AEs related to intraocular inflammation

Treatment of AEs related to an intraocular inflammation will be described with number of patients using corticoids (None/local CS alone/systemic CS alone/ local and systemic in association) for the first 6 months of follow-up and for the follow-up between 6 months and 1 year and for each year of follow-up after the first year. Number and percent of inflamed eyes with at least 7 days of CS treatment will be described for each type of CS (local CS alone/systemic CS alone/ local and systemic in association) for the first 6 months of follow-up and for the follow-up between 6 months and 1 year and for each year of follow-up after the first year.

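### Local corticosteroid and IOP-lowering use is counted per patient, which attenuates the randomised second-eye GS010-versus-placebo difference in treatment burden; add an eye-by-arm table for AE-driven local use

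*SAP*

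**What the plan says.** **Design.** Protocol 9.1 gives GS010 to the first affected eye in both arms. The second eye receives GS010 in TARM1 and placebo in TARM2.

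**Medication tables (SAP 11).** The general rule is "Concomitant treatments will be summarized by coded terms using number and percentage of Safety population subjects by treatment group". Corticosteroid route is also a patient attribute: "A patient will be counted in the “local and systemic corticosteroid” class if he took, during the time windows of interest" at least one of each type. Local steroid is described by duration, reason and ocular or non-ocular indication. IOP-lowering agents are described by duration and "Reason of use of intraocular pressure lowering agents (Preventive of intraocular pressure increase / for AE". No split by first and second eye is stated for any of these.

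**Treatment of adverse events (SAP 14.1.6 and 14.1.7).** For raised pressure: "Treatment of AEs with elevation of IOP will be described with number of patients using IOP lowering treatment". For inflammation: "Treatment of AEs related to an intraocular inflammation will be described with number of patients using corticoids". Section 14.1.7 adds one eye-level item, the number and percentage of inflamed eyes with at least 7 days of steroid, by route and period. It names no arm or eye-order split. Section 14.1.5 promises a summary of medications given for inflammation and IOP events without stating the unit.

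**The events themselves (SAP 14.1).** "Ocular TEAEs will be summarized by treatment group for the first affected eye and second-affected/not-yet-affected eye separately". Sections 14.7.1 and 14.7.2 also report IOP and slit-lamp findings by treatment group for each eye.

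**Preventive steroid (Protocol 13.9.1).** "All subjects will receive a peri-treatment systemic oral immune modulating regimen". It starts two days before the first injection and lasts 28 days.

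**The concern.** Local steroids and pressure-lowering drops are given to an eye. In a patient-level table, a TARM2 patient treated because of the GS010 first eye is counted as a user even if the placebo eye needed nothing. The second eye changes a patient's classification only when the first eye went untreated. Protocol 14.2 says inflammation occurs in most subjects given intravitreal GS010. A high first-eye rate is the condition under which a patient-level any-use table compresses the arm difference most.

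Secondary objective 1 concerns the safety and tolerability of bilateral and unilateral injection. The drug burden in the second eye is the cost of the additional GS010 injection, and it has a randomised placebo comparator. As written, the SAP shows ocular events by eye and arm but does not require the local drugs given for them to be shown the same way, so the two cannot be lined up.

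There is a second, smaller problem. The oral regimen begins before the first injection and continues after it, so it is concomitant under SAP 11. In the first 6 months every compliant subject is therefore a systemic user in the route table.

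**Working it through.** **Inputs.** The documents give no rate of local steroid or IOP-lowering use, so there is no figure of the plan's own to reproduce. All rates below are assumptions. Let g be the probability that a GS010 eye uses a local agent (taken as equal for first and second eyes) and p that for a placebo eye, with g > p. I read the patient-level tables as presented by arm.

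**Second-eye contrast.** g - p.

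**Patient-level any use, independent eyes.**
- TARM1: 1 - (1-g)²
- TARM2: 1 - (1-g)(1-p)
- Difference: (1-g)(1-p) - (1-g)² = (1-g)(g-p)

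The table keeps only the fraction (1-g) of the second-eye difference.

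**Patient-level any use, full concordance.** Second-eye users all lie within the first-eye users, so both arms show g and the difference is 0.

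| g | p | Second eye (points) | Per patient, independent eyes | Per patient, full concordance |
|---|---|---|---|---|
| 30% | 10% | 20 | 51% v 37%: 14 | 0 |
| 50% | 10% | 40 | 75% v 55%: 20 | 0 |
| 60% | 5% | 55 | 84% v 62%: 22 | 0 |
| 70% | 10% | 60 | 91% v 73%: 18 | 0 |
| 90% | 10% | 80 | 99% v 91%: 8 | 0 |

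**Range for g = 40-80% and p = 2-10%.**
- Second-eye difference: smallest 40 - 10 = 30 points, largest 80 - 2 = 78 points.
- Per patient with independence, smallest: g = 0.80, p = 0.10 gives 0.20 × 0.70 = 0.14.
- Per patient with independence, largest: for fixed p the product peaks at g = (1+p)/2. At p = 0.02 that is g = 0.51, giving 0.49 × 0.49 = 0.24.
- So 30-78 points becomes 14-24 points, or 0 with full concordance. A partly concordant case lies between: at g = 70%, p = 10%, halfway between the two extremes, the per-patient difference is 80.5% - 71.5% = 9 points.

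**The inflamed-eye count in 14.1.7.** Its denominator is eyes that became inflamed, which is itself a post-treatment outcome. Even if split by arm and eye, it would give steroid use among inflamed eyes and not burden per treated eye.

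**The 0-6 month route table.** SAP 11 counts as concomitant any drug started before the first injection and continued after it. A 28-day regimen starting two days before injection meets that rule. All compliant subjects then fall in a class with systemic use, and the local-only class holds at most those who did not take the regimen.

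**The case against.** The strongest reply has five parts.

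1. *The patient-level table answers a legitimate question.* Bilateral versus unilateral is a subject-level regimen, and the arm comparison of it is randomised and valid. This stands. The patient-level difference is a different quantity from the second-eye difference, not an erroneous one. SAP 14 also plans no statistical comparison of safety unless specified, so no inference is distorted.

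2. *The second-eye picture is not lost.* A reader might infer that the contrast is hidden altogether. The documents do not support that: ocular events, IOP and inflammation scores are shown by eye and arm, and SAP 11 provides listings of patients on these drugs. What is not required is a summary of local medication by eye and arm.

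3. *Systemic rescue can be found.* A reader of the route table might infer that it cannot be seen at all. That goes too far. SAP 11 describes systemic steroid by reason (preventive or for an AE), and 14.1.7 is confined to treatment of inflammation events. Only the route-incidence table fails to show it.

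4. *Mandated prevention is the same in both arms.* This stands. The oral steroid goes to every subject and an IOP-lowering agent precedes every injection, so required preventive use holds no GS010-versus-placebo contrast. It also limits the remedy. Where the pre-injection agent is local and counts as concomitant under SAP Appendix 2, any-use over all treated eyes would approach 100% in every eye group.

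5. *The table templates might already split by eye.* SAP section 7 refers to templates that are not among the documents. One therefore cannot say that the 14.1.7 count will not be split, only that the text does not state a split.

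**Conclusion.** The point holds as attenuation of a descriptive safety contrast. SAP 11, 14.1.6 and the main 14.1.7 count work per patient, and with a GS010 first eye in both arms they reduce the second-eye difference g-p to (1-g)(g-p) under independence and to 0 under full concordance. Reduction follows for any g > p with g > 0 under either dependence assumption. Its size depends on use rates that the documents do not give and on similar GS010-eye rates for first and second eyes. Under the assumed 40-80% and 2-10%, 30-78 points becomes 14-24 points or 0.

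The route-table problem is confined to one period of one table: the local-only class is essentially empty for 0-6 months, and AE-driven systemic use has to be read from other planned outputs. Neither problem affects the primary analysis or makes an existing table wrong. The change is worth making because it matches the medication display to the event display at little cost.

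**What to change.** - **Add** to SAP 11, 14.1.6 and 14.1.7 a table of AE-driven local corticosteroid use and AE-driven local IOP-lowering use (any use and duration), by arm for the first and second eye separately, with all treated eyes as denominator.
- **Separate prevention.** Show preventive local use, including the pre-injection IOP-lowering agent, in its own row so that it does not swamp the AE-driven figures.
- **State** the arm and eye-order split for the inflamed-eye count in 14.1.7.
- **Keep** systemic agents and the existing bilateral-versus-unilateral tables per subject.
- **Route table in SAP 11:** show the mandated oral regimen as its own row, so that the classes reflect other corticosteroid use.

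**Cost.** SAP wording and a few additional descriptive tables, with no change to treatment rules. The condition is that the treated eye is available for each local medication. The eye-level count in 14.1.7 implies this, but the documents do not say so, and Protocol 14.4 on recording concomitant medications does not mention the eye. Confirm that in the eCRF first.
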